8.1 Anticipated Clinical Benefits

Potential benefits associated with participation in the clinical investigation include:

- Helping to find better treatments, therapies and/or diagnostic tests in the area of hearing loss or other condition
- The opportunity to be given a new intervention that may be better for their condition or that has fewer side effects or limitations than they are receiving now
- The opportunity to access the newest innovations in the treatment of hearing loss
- The chance to play an active role in their own hearing health and gain a greater understanding of their condition
- Advice, care, and support from trained clinical staff who understand hearing loss or their condition
- Closer monitoring of their hearing loss or condition

8.2 Anticipated Adverse Device Effects

Based on the available safety reference information and literature, the potential clinical risks have been documented below.

8.2.1 Risks Associated with the Surgery

- General risks associated with surgery including pain, scarring, bleeding and infection
- General risks associated with anesthesia during the surgery (e.g., risks for the heart, lungs, kidneys, liver, and brain) which, in rare cases, can result in death

8.2.2 Additional Risks Associated with Implantation of the Study Device

- Pain or discomfort
- Skin irritation near the implant, swelling or redness near the magnet site, skin breakdown
- Sense of numbness or stiffness in the area of the surgery
- Failure of the implant to properly anchor to the skull-bone due to a lack of adequate bone quantity/quality, trauma, infection, generalized diseases and surgical complications
- Other medical complications that may require additional medical treatment, such as:
 - Concurrent CSF leakage: a leak of CSF (cerebrospinal fluid) through the hole in the skull
 - Subdural injury: blood vessels near the brain may burst
 - Subcutaneous hematoma: bruises and contusions on the skin
 - Skin-flap infection, irritation or inflammation
 - Extrusion of the device caused by a foreign body under the skin
 - Revision surgery to remove the study implant in the event of device failure
- Failure of the implant or sound processor could result in the perception of an uncomfortably loud sound sensation, intermittent sound, or no sound.
- The implanted magnet may affect MRI (Magnetic Resonance Imaging) procedures. The magnet may influence the MRI scanner or the ability of the scanner to detect certain changes. Under certain circumstances removal of the AMDT may be necessary prior to MRI scanning.
- There may be side effects that are not known at this time.

8.3 Risks Associated with Participation in the Clinical

Investigation

In addition to the anticipated surgical and adverse device effects of the AMDT, the following risks may also present when participating in the clinical investigation:

- Exposure to sounds produced in the test battery that could be perceived as too loud
- Testing procedures that may produce anxiety or fatigue
- Discomfort and potential abrasion to the ear canal due to placement of insert earphones
- Discomfort associated with the fitting of the Sound Arc

8.4 Risk Mitigation

The clinical investigation sites chosen for participation in the study have been previously trained as part of the Sponsors Controlled Market Release (CMR). Each have experience treating the indicated population with the AMDT.

The study design introduces minimal risk outside of the standard commercial risks associated with bone conduction technology. Additionally, all reported device or procedure related adverse events and device deficiencies captured during the course of the study will be regularly reviewed by the Sponsor's Clinical Review Board to facilitate early detection and appropriate intervention if events are unanticipated with respect to incidence, severity, or outcome. Device associated adverse events and deficiencies will also be entered into our Global Quality Complaint Management System to allow for post market trending and any applicable reporting to regulatory authorities.

8.5 Risk-to-Benefit Rationale

The subjects recruited for this study are already considering treatment with an osseointegrated bone conduction device. The risk benefit rationale is such that participation in this study will provide subjects with additional hearing health information pertaining to their outcome with the Osia 2 bone conduction system than they would receive commercially.

9 STATISTICAL CONSIDERATIONS

9.1 General Considerations

Except where otherwise specified, the following general principles apply to the planned statistical analyses. All statistical analysis will be conducted using [REDACTED]
[REDACTED] or other widely-accepted statistical or graphical software as required.

Continuous data will be summarized with mean, standard deviation, median, minimum,

maximum, and number of evaluable observations. Categorical variables will be summarized with frequency counts and percentages. Confidence intervals may be presented, where appropriate, using the t-distribution for continuous data and Clopper-Pearson Exact method for categorical variables.

All investigational sites will follow the requirements of a common protocol and standardized data collection procedures and forms. All efforts will be put forth to ensure near complete follow-up, with particular focus on the assessment of the primary outcome and occurrence of adverse events. Regular reminders of subject follow-up due dates will be provided to participating centers to facilitate scheduling of follow-up visits. Further details regarding statistical considerations can be found in the Statistical Analysis Plan.

9.2 Endpoints

9.2.1 Primary Endpoint

To demonstrate significant difference between the aided and unaided conditions at 3 months using an adaptive speech in noise test when compared to the preoperative (Visit 1) unaided condition.

9.2.2 Secondary Endpoint

The secondary endpoint is to evaluate the safety of the Osia 2 system in a group of adult newly implanted recipients by estimating the incidence of device or procedure related adverse events.

9.2.3 Exploratory Endpoints

There are no exploratory endpoints.

9.3 Hypotheses

Formal hypothesis tests are planned for the primary endpoint to establish superiority of the aided over unaided conditions. Statistical hypothesis tests will be based on t-tests with a one-sided 0.025 alpha level.

9.3.1 Primary Hypothesis

The primary objective is to evaluate the performance of the Osia 2 system on an adaptive speech in noise test. A t-test of superiority for the adaptive speech in noise test, comparing the aided and unaided conditions at 3-months relative to the preoperative (Visit 1) unaided condition. The mathematical statement of this hypothesis test is written as:

$$H_0: \Delta On \geq \Delta Off \quad H_1: \Delta On < \Delta Off$$

where ΔOn is the mean change in the adaptive speech in noise test between the 3-month aided (on) condition and the preoperative unaided condition, and ΔOff is the mean change in the adaptive speech in noise test between the 3-month unaided condition (off) and the

preoperative (Visit 1) unaided condition. Successful rejection of the null hypothesis indicates the aided performance of the Osia 2 system is superior to the unaided performance based on the adaptive speech in noise test.

9.3.2 Secondary Hypothesis

There is no secondary hypothesis as the intent is to capture the observed rate of incidence for device and procedure related adverse events.

9.3.3 Exploratory Hypothesis

There are no exploratory hypotheses.

9.4 Sample Size Determination

The planned sample size of 20 will provide greater than 95% power under a conservatively assumed mean of 12 and standard deviation of 15. Calculations are based on a one-sided 0.025 alpha and include allowance for attrition of up to 20%.

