7.2.6 Criteria for Subject Withdrawal

Subjects can decide to withdraw from the investigation at any time. The Investigator shall ask the reason(s). The reason for withdrawal should be documented in the subject's source files and the case report form (CRF).

The Investigator or Sponsor may also decide to withdraw a subject from the clinical investigation if it is considered to be in their best interests.

Subject withdrawal may be for any of the following reasons:

- Adverse Event (AE)

- Device Deficiency (DD)
- CIP or GCP deviation
- Subject lost to follow-up
- Subject withdrew consent
- Subject death
- Sponsor decision
- Investigator decision
- Other (specify)

If subject withdrawal is due to problems related to the AMDT or comparator safety or performance, the Investigator shall ask for the subject's permission to continue in safety follow up (i.e., adverse events) until their scheduled End-of-Study visit.

If a subject is lost to follow-up, every possible effort must be made by the study site personnel to contact the subject and determine the reason for discontinuation. At least 3 separate attempts taken to contact the subject may be documented in the medical chart.

Treated subjects who are withdrawn/discontinued will not be replaced.

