9.6 Primary Endpoint Analyses

Analysis of the primary endpoint will be based on a paired t-test of means comparing the change from preoperative (Visit 1) between the 3-month aided and unaided conditions. This will be a superiority test based on a one-sided 0.025 alpha level. Sensitivity analyses will include testing for a period and for a crossover effect.

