4.3 Study Assessments

The statistical analyses for the primary objective will be based on the 3-month assessment compared to the pre-operative baseline assessment. Analyses for the secondary objective will be based on safety data collected at the time of treatment and for the duration of the study up to and including 6 months.

Statistical Analysis Plan		Page 8 of 13
Sponsor Cochlear Americas	Study A post-market interventional cohort study evaluating the clinical efficacy of the Osia 2 system in the US Market	Version 3.0

5 Sample Size Determination

The planned sample size of 20 will provide greater than 80% power under a conservatively assumed mean of 12 and standard deviation of 15. Calculations are based on a one-sided 0.025 alpha and include allowance for attrition of up to 20%.

The primary objective is to evaluate the performance of the Osia 2 system on an adaptive speech in noise test. A paired t-test of superiority for the adaptive speech in noise test, comparing the aided and unaided conditions at 3-months relative to the preoperative (Visit 1) unaided condition. The mathematical statement of this hypothesis test is written as:

$$H_0: \Delta On \geq \Delta Off$$

$$H_1: \Delta On < \Delta Off$$

where ΔOn is the mean change in the adaptive speech in noise test between the 3-month aided (On) condition and the preoperative (Visit 1) unaided condition, and ΔOff is the mean change in the adaptive speech in noise test between the 3-month unaided condition (Off) and the preoperative (Visit 1) unaided condition. Successful rejection of the null hypothesis indicates the aided performance of the Osia 2 system is superior to the unaided performance based on the adaptive speech in noise test.

The secondary objective is to evaluate the safety of the Osia 2 system in a group of adult newly implanted recipients. Descriptive statistics specifically counts and percentages of device or procedure related adverse events captured through 6 months post-surgery will be summarized.

6 Statistical Analyses

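### Protocol 9.4 claims more than 95% power, but its own inputs give about 85% after the stated attrition and 92% with none; SAP section 5 says more than 80% for the same inputs

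*Protocol*

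**What the plan says.** Protocol 9.4 reads: "The planned sample size of 20 will provide greater than 95% power under a conservatively assumed mean of 12 and standard deviation of 15". It continues: "Calculations are based on a one-sided 0.025 alpha and include allowance for attrition of up to 20" per cent.

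SAP section 5 gives the same sample size, mean, standard deviation, alpha and attrition allowance, but its claim is: "The planned sample size of 20 will provide greater than 80% power under a conservatively assumed mean of 12 and standard deviation of 15". The SAP introduction says it was developed with respect to protocol Version 3.0. It gives no reason for the different power.

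Protocol 9.6 fixes the test, with the unaided score as the other member of each pair: "Analysis of the primary endpoint will be based on a paired t-test of means comparing the change from preoperative (Visit 1) between the 3-month aided". SAP 6.6.1.1 also specifies a paired t-test. On losses, Protocol 7.2.6 says: "Treated subjects who are withdrawn/discontinued will not be replaced".

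**The concern.** Two documents describe one design with identical inputs and state different power. Both figures are lower bounds, so they do not strictly exclude each other, and a calculation is needed to see which one the inputs support. A standardized effect of 12/15 = 0.8 with at most 20 pairs looked too small for more than 95% power at one-sided 0.025, above all once a fifth of the subjects may be lost without replacement.

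Protocol 7.2.3 relies on this calculation when it calls the sample size adequate under conservative assumptions, and the protocol is the document sent to ethics committees (Protocol 16). The study is meant to supply reimbursement evidence after earlier evidence was judged inadequate (Protocol 4.1 and 4.2). Readers of the protocol are told that the chance of missing the assumed effect is below 5%.

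**Working it through.** **Inputs**
- Sample size 20, mean 12, standard deviation (SD) 15, one-sided alpha 0.025, attrition up to 20%: Protocol 9.4, repeated in SAP section 5.
- Paired t-test: Protocol 9.6 and SAP 6.6.1.1.
- Losses not replaced: Protocol 7.2.6. The evaluable number at full attrition is 20 × 0.8 = 16.
- Assumption: 15 is the SD of the within-subject difference. Neither document says so.

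**What is tested.** Both changes are taken from the same preoperative unaided score, which cancels in ΔOn − ΔOff. The paired difference is therefore the 3-month aided score minus the 3-month unaided score. The mean of 12 is read as the size of that difference in the favourable direction.

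**Formula.** Power = P(T > t₀.₉₇₅,ₙ₋₁), where T is noncentral t with n − 1 degrees of freedom and noncentrality (12/15)√n = 0.8√n.
- n = 16: noncentrality 0.8 × 4 = 3.20; power **84.8%**.
- n = 20: noncentrality 0.8 × 4.472 = 3.578; power **92.4%**.

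**Attempts to reproduce more than 95%**

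| Calculation | n = 16 | n = 20 |
|---|---|---|
| Exact paired t, one-sided 0.025 | 84.8% | 92.4% |
| Exact paired t, two-sided 0.05 | 84.8% | 92.4% |
| Normal approximation, one-sided 0.025 | Φ(3.20 − 1.96) = 89.3% | Φ(3.578 − 1.96) = 94.7% |
| Exact paired t, one-sided 0.05 (not the stated alpha) | 92.0% | 96.4% |

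No calculation at the stated alpha exceeds 95%. The nearest is the normal approximation with no attrition. It rounds to 95% but is not above it, and it leaves out the attrition that the section says is included. The only entry above 95% contradicts both the stated alpha and the attrition allowance.

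**SAP figure.** More than 80% is reproduced: 84.8% at n = 16. An 80% target needs 15 evaluable subjects, and 15/0.8 = 18.75, so 19 implanted.

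**What 95% would take.** Exact power is 94.7% at 22 evaluable subjects and 95.6% at 23. With 20% attrition, 23/0.8 = 28.75, so 29 implanted. With the mean kept at 12, the SD would have to be at most about 12.4 at n = 16, or 14.1 at n = 20.

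**If 15 were the SD within each condition.** The SD of the difference would be 15√(2(1 − r)), where r is the within-subject correlation. No value of r is given, so a range is shown.

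| r (assumed) | n = 16 | n = 20 |
|---|---|---|
| 0 | 56.2% | 67.0% |
| 0.25 | 68.6% | 79.1% |
| 0.5 | 84.8% | 92.4% |
| 0.6 | 91.6% | 96.6% |
| 0.7 | 97.1% | 99.2% |

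More than 95% would need r above about 0.66 at n = 16, or above about 0.56 at n = 20.

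**The case against.** The strongest reply is that the plan never defines its SD. It gives only a "conservatively assumed mean of 12 and standard deviation of 15". If 15 is a per-condition value and aided and unaided scores correlate strongly enough, the protocol figure can be reached. That is true, but it needs a correlation that neither document states. A single mean and SD quoted for a paired t-test most naturally describe the paired difference. What stands is that the results depend on this reading and that the plan should define the SD.

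Second, attrition is stated as a maximum, so a 15% type II error is the worst case allowed for. This is fair: it is 7.6% with no losses and 10.8% with two (n = 18, power 89.2%). Even the best case misses the claim.

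Third, multiple imputation over all implanted subjects (Protocol 9.5, SAP 6.2 and 6.6.1.2) means that the analysis is not simply one of 16 completers, although SAP 6.6.1.1 refers to complete data. Imputation would not be expected to raise power above the 92.4% for 20 complete pairs.

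Finally, more than 80% and more than 95% can both be true as lower bounds, and the SAP statement is true on these numbers. The error therefore lies in the protocol sentence. The test, alpha, sample size and decision rule are unaffected.

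**Conclusion.** The concern holds. Under the natural reading of its inputs, the protocol claims power that the design does not have: 84.8% at the stated attrition and 92.4% with none, against more than 95%. At full attrition the type II error is 100 − 84.8 = 15.2%, about three times the 5% ceiling implied. The SAP's lower figure is the one that the inputs support.

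This rests on the paired t-test as planned, one-sided alpha 0.025, and 15 being the SD of the paired difference. On that footing the trial still meets an 80% standard and the adequacy claim in Protocol 7.2.3 survives. The figure in Protocol 9.4 must be corrected and reconciled with SAP section 5.

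**What to change.** In Protocol 9.4, replace the power statement with wording such as: with 20 subjects implanted, a mean paired difference of 12 and an SD of the paired difference of 15, a one-sided 0.025 paired t-test has about 85% power with 16 evaluable subjects (20% attrition) and about 92% if all 20 are evaluable. Put the same sentence in SAP section 5. The SAP's bound is not wrong, but identical wording removes the discrepancy.

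If the sponsor worked from a per-condition SD and a correlation, both documents should state these and show the calculation instead.

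The cost is one sentence in each document and a less favourable stated power. No change in sample size, test or data collection is needed.

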9.5 Analysis Populations

Analysis will be based on the intent-to-treat population. In order to obtain a complete ITT population, multiple imputation will be used for any missing outcome data.

9.6 Primary Endpoint Analyses

Analysis of the primary endpoint will be based on a paired t-test of means comparing the change from preoperative (Visit 1) between the 3-month aided and unaided conditions. This will be a superiority test based on a one-sided 0.025 alpha level. Sensitivity analyses will include testing for a period and for a crossover effect.

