7.1.1 Design Rationale

This clinical investigation design ensures that the results obtained have clinical relevance, scientific validity and address the clinical investigation objectives. A within subject research design has been employed to utilize each subject as his or her own control as it accommodates the heterogeneity that characterizes hearing impaired populations.

Subjects seeking treatment with an Osia 2 bone conductive device may present clinically as being aided or unaided, therefore it is important to capture both listening conditions to ensure a representative sample. Since the Osia 2 Sound Processor cannot be utilized in a non- surgical wearing configuration, each subject will be fit with the Baha 5 Power device on a Baha Sound Arc according to the Cochlear Baha Fitting prescription. The Baha 5 Power device is most comparable from a sound processing perspective to the Osia 2 Sound Processor.

A test order randomization paradigm has been employed to minimize test order effects and demonstrate the unaided to aided benefits of bone conduction technology. Due to the physiology of a conductive or mixed conductive hearing loss, there are no carry-over effects associated with the use of an osseointegrated bone conduction intervention and therefore comparisons can be made.

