6.11	Protocol Deviations	13
7	Changes from Planned Analyses.....	13
8	Subject Listings	13

Statistical Analysis Plan		Page 6 of 13
Sponsor Cochlear Americas	Study A post-market interventional cohort study evaluating the clinical efficacy of the Osia 2 system in the US Market	Version 3.0

1 Introduction

This statistical analysis plan (SAP) describes the planned statistical methods to be used during the reporting and analysis of data collected under the Clinical Investigation Protocol; A post-market interventional cohort study evaluating the clinical efficacy of the Osia 2 system in the US Market. This SAP should be read in conjunction with the study clinical investigation plan (CIP) and case report forms (CRFs). This version of the SAP has been developed with respect to the Clinical Investigation Protocol A post-market interventional cohort study evaluating the clinical efficacy of the Osia 2 system in the US Market, Version 3.0 June 19, 2020. Any revisions to the protocol or CRFs that impact the planned analyses may require updates to the SAP.

2 Abbreviations

Abbreviation/Term	Definition
ADE	Adverse Device Effect
AE	Adverse Event
CIP	Clinical Investigation Plan
CRF	Case Report Form
DD	Device Deficiency
eCRF	Electronic Case Report Form
SADE	Serious Adverse Device Effect
SAE	Serious Adverse Event
SAP	Statistical Analysis Plan
UADE	Unanticipated Adverse Device Effect
USADE	Unanticipated Serious Adverse Device Effect

3 Study Objectives

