4.1 Randomization

Test order for the 3-month interval will be randomly assigned in a 1:1 allocation ratio, stratified by site. Test order will be either aided followed by unaided, or unaided followed by aided.

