6.6.1.1 Primary Analysis

A paired t-test of superiority for the adaptive speech in noise test, comparing the aided and unaided conditions at 3-months relative to the preoperative (Visit 1) unaided condition. The mathematical statement of this hypothesis test is written as:

$$H_0: \Delta On \geq \Delta Off$$

$$H_1: \Delta On < \Delta Off$$

where ΔOn is the mean change in the adaptive speech in noise test between the 3-month aided (On) condition and the preoperative (Visit 1) unaided condition, and ΔOff is the mean change in the adaptive speech in noise test between the 3-month unaided condition (Off) and the preoperative (Visit 1) unaided condition. Successful rejection of the null hypothesis indicates the aided performance of the Osia 2 system is superior to the unaided performance based on the adaptive speech in noise test.

The endpoint will be assessed in the ITT analysis cohort with complete data preoperatively and at 3 months.

Statistical Analysis Plan		Page 11 of 13
Sponsor Cochlear Americas	Study A post-market interventional cohort study evaluating the clinical efficacy of the Osia 2 system in the US Market	Version 3.0

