6.6.1.2 Handling of Missing Data

In the event there are missing primary endpoint data the primary endpoint will be analyzed using a multiple imputation analysis. SAS PROC MI will be used to produce 100 imputed datasets. The imputed variable will be the difference between aided and unaided conditions at 3 months in the change in adaptive speech in noise test from preoperative. The following variables will be used as predictors in the model:

- Age
- Sex
- Pre-operative unaided adaptive speech in noise test

The estimates for the mean difference between aided and unaided change from pre-implant will be combined using PROC MIANALYZE providing an overall estimate for the primary endpoint, 95% confidence interval and one-sided p-value.

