6.6.3 Supporting Analyses

Additional supporting data collected in each cohort includes the following:

- Concomitant medications
- Bone conduction
- Sound field thresholds
- Speech perception testing in quiet and noise
- SSQ 12
- Patient Reported Questionnaire

Statistical Analysis Plan		Page 12 of 13
Sponsor Cochlear Americas	Study A post-market interventional cohort study evaluating the clinical efficacy of the Osia 2 system in the US Market	Version 3.0

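### Does the SAP's silence on the protocol's period and crossover tests of Month 3 test order leave the analysis open to error?

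*Protocol*

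**What the plan says.** Protocol 9.6 makes the primary analysis a paired t-test of the aided and unaided conditions at 3 months, each taken as a change from the preoperative unaided score. It then adds: "Sensitivity analyses will include testing for a period and for a crossover effect". Protocol 9.1 refers the reader onward: "Further details regarding statistical considerations can be found in the Statistical Analysis Plan".

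SAP 4.1 describes the randomization behind those tests: "Test order for the 3-month interval will be randomly assigned in a 1:1 allocation ratio, stratified by site". The two orders are aided first and unaided first. SAP 6.6.1.1 then gives "A paired t-test of superiority for the adaptive speech in noise test" and restricts the endpoint to ITT subjects with complete preoperative and 3-month data. SAP 6.6.1.2 imputes the aided-minus-unaided difference when it is missing. After "The following variables will be used as predictors in the model" it lists age, sex and the preoperative unaided score. Test order is not listed.

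SAP 6.6.3 ("Additional supporting data collected in each cohort includes the following") lists data types but no order analysis. Nor do the sections on poolability, subgroups and safety contain one. SAP section 7 does not record the two tests as dropped. SAP section 1 says the SAP is to be read together with the protocol.

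On carry-over, Protocol 7.1.1 says "there are no carry-over effects associated with the use of an osseointegrated bone conduction intervention".

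**The concern.** The protocol promises two analyses and sends the detail to the SAP, and the SAP contains neither. An analyst working from the SAP alone could miss them, or choose a model and analysis set after seeing the data. The crossover test is vaguer still. The term is undefined, the protocol asserts that carry-over is absent, and the usual carry-over contrast needs the aided-plus-unaided sum, which the SAP does not impute.

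There is also a technical trap. If missing differences are imputed without test order, the imputed values are drawn toward the mean of both orders combined. A period test on the completed data then sees a diluted order effect and errs toward reassurance. The period check is the only planned analysis that would show whether test order moved the result, and the study is unblinded, so a diluted check would matter if it were the one actually run.

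**Working it through.** **Inputs.** N = 20, mean difference 12, SD 15, one-sided alpha 0.025, attrition up to 20% (Protocol 9.4, SAP 5). SD 15 is taken as the SD of the aided-minus-unaided difference. Let π be the effect of being tested second, so that the mean difference is 12 + π in one order and 12 − π in the other. The sign of the treatment effect does not matter here. The documents give no value for π; 0 to 5 units is assumed. Order is taken as 10:10 before any loss, with data missing at random.

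**The plan's own figure.** No power is stated for the sensitivity tests. For the primary test at n = 16, the noncentral t with noncentrality (12/15)√16 = 3.2 and 15 df gives 84.8%. That agrees with the SAP's claim of more than 80%. The protocol's figure of more than 95% does not reproduce, but that is a separate matter and nothing below uses it.

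**Effect on the primary test.** The preoperative score cancels, since (aided − pre) − (unaided − pre) = aided − unaided. With n1 and n2 subjects observed in the two orders and n = n1 + n2, the estimate shifts by π(n1 − n2)/n. With 4 of 20 missing:

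| Missing by order | Probability | Shift |
|---|---|---|
| 2:2 | 41.8% | 0 |
| 3:1 | 49.5% | 2/16 = 0.125π |
| 4:0 | 8.7% | 4/16 = 0.25π |

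The expected shift is 0, because either order is equally likely to lose more subjects. The mean absolute shift is 0.495 × 0.125π + 0.087 × 0.25π = 0.084π. That is 0.25 units at π = 3 and 0.42 at π = 5, against a standard error of 15/√16 = 3.75.

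**Attenuation if the period test used data imputed without order.** Imputed values centre on the overall observed mean. The order coefficient is then multiplied by [n − (n1 − n2)²/n]/20.

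- 2:2: 16/20 = 0.80
- 3:1: (16 − 4/16)/20 = 0.7875
- 4:0: (16 − 16/16)/20 = 0.75
- Average with 4 missing: 0.789
- Average with 3, 2, 1 and 0 missing: 0.84, 0.89, 0.95 and 1

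The loss therefore needs both substantial missingness and a choice to use the imputed data.

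**Which data the plan points to.** Protocol 9.5 and SAP 6.2 call for multiple imputation to complete the ITT population. SAP 6.3 imputes the primary endpoint and otherwise lets a missing value drop out of the analysis concerned. SAP 6.6.1.1 speaks of complete data. No sentence assigns the sensitivity tests to the imputed sets.

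**Period test rejection rates, two-sided 5%, 4 of 20 missing at random.** The imputed rows come from simulation (8,000 replicates, 100 imputations, Rubin's rules with small-sample df, three uninformative predictors). The complete-case row is the noncentral t averaged over the three splits.

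| Analysis set | π = 0 | π = 3 | π = 5 |
|---|---|---|---|
| Imputed, order omitted | 0.5% | 1.7% | 4.4% |
| Imputed, order included | 3.4% | 7.6% | 17% |
| Complete cases | 5% | 11.5% | 23.5% |

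Complete cases hold the nominal size and have the most power. Adding order to the imputation model would give a weaker test than not imputing at all.

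**What either check can show.** At 8:8 the 95% half-width for π is 2.145 × 3.75 = 8.04 units, wider than the whole assumed range. For the crossover contrast, the SD of the aided-plus-unaided sum is 15√((1+ρ)/(1−ρ)). That is 15 to 45 for an assumed correlation ρ of 0 to 0.8, and the half-widths are 16 to 48 units.

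**The case for a change.** The case for changing the SAP is that a sensitivity analysis should be fixed before the data are seen. The protocol expressly defers to the SAP, and the SAP gives no model, contrast or analysis set. The ITT rule can fairly be read as covering every outcome analysis, and on that reading the period test is biased toward finding nothing. The crossover test cannot be run on the imputed data at all, because only the difference is imputed.

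The textual part stands. The SAP is silent, the crossover term is undefined, and the analysis set is not stated for these tests. The attenuation is also real arithmetic wherever its conditions hold.

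The claim that this harms the trial does not stand. The imputation reading is one of two, and the other is at least as natural. The crossover test's inability to use the imputed data simply sends it to complete cases, where the period test also works best. Both conditions are tested at the same visit, so order at that visit cannot cause dropout before it; unequal loss between orders would be chance. Stating that carry-over is not expected and then checking for it is ordinary practice, so Protocol 7.1.1 and 9.6 do not conflict.

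**Conclusion.** No change is needed. This is missing detail that a competent analyst supplies in the standard way. The period test compares the aided-minus-unaided difference between the two orders, and the crossover test compares the aided-plus-unaided sum, both in subjects with complete Month 3 data. The commitment survives in Protocol 9.6, and the SAP says it is read with the protocol.

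The primary paired t-test, its alpha and its power are untouched. Its expected shift from test order is 0, and the mean absolute shift is about 0.084π with 4 of 20 missing, or 0.25 to 0.42 units for π of 3 to 5 against a standard error of 3.75. The attenuation of about 21% arises only with 4 missing and only if the test is run on data imputed without order. It is about 5% with 1 missing and nil with none. Fuller specification would not make either check informative at this sample size.

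This rests on SD 15 applying to the difference, π of no more than about 5 units, 10:10 allocation, and data missing at random with respect to order. A much larger order effect with markedly uneven loss between orders would give the point more weight, but nothing in the documents suggests either.
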